#### **C. Data Collection**

1. After written consent is obtained, the study coordinator will assign the participant a randomized study number to de-identify the participant.

2. To achieve our project's goal, we will have 4 separate groups (OMT, BEMER, OMT+BEMER, and Combined Placebo of OMT+ Sham BEMER). All treatments will be performed by osteopathic medical students. [name] will provide students

- additional training on OMT and placebo treatments, and [name], a BEMER representative, will provide additional training on BEMER treatments.
3. To control for anchoring bias, subjects will be randomized into one of the four groups: OMT, BEMER, OMT+BEMER, and Placebo.
- D. Osteopathic Manipulation Diagnosis and Treatment Protocol (OMT)
1. Osteopathic Diagnosis and Screening
    - a) Screening Special tests: Spurling's test, Wallenberg test
    - b) Observe and Palpate Cervical and Thoracic spine muscles for TART (tissue texture change, asymmetry, restriction of motion, and tenderness) changes- AROM and PROM of the cervical spine (using head and neck motion for T1-4)
    - c) OA (atlanto-occipital joint), AA (atlanto-axial joint), C2-C7 (cervical vertebrae 2-7), and T1-4 (thoracic vertebrae 1-4) intersegmental diagnosis
    - d) TMJ (temporomandibular joint) assessment – opening and closing of jaw
    - e) Counterstrain Tenderpoint screening for the following muscles: Medial pterygoid, Anterior C7, Anterior C8, Posterior C1 inion
    - f) 1st rib somatic dysfunction
  2. Osteopathic Manipulative Treatment/Techniques
    - a) Suboccipital Release (constant inhibitory pressure), supine – myofascial release/soft tissue technique
    - b) Contralateral Traction, supine - soft tissue technique
    - c) Upper thoracic spine unilateral prone pressure, prone - soft tissue technique
    - d) Direct or Indirect Thoracic inlet/outlet, supine – myofascial release technique
    - e) Occipitoatlantal somatic dysfunction muscle energy (post-isometric relaxation) supine
    - f) Atlantoaxial somatic dysfunction muscle energy technique (post-isometric relaxation) supine
    - g) C2-C7 somatic dysfunction muscle energy technique (post-isometric relaxation) supine
    - h) T1-4 Dysfunction muscle energy technique (post-isometric relaxation) - seated
    - i) 1st rib elevation dysfunction – articular technique – seated
    - j) Direct or indirect Sub mandibular release, supine - myofascial release technique

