  - b) Each subject in the OMT groups (i.e. OMT and OMT+BEMER) will receive treatment 3 times per week for a period of 3 weeks. As previously mentioned, subjects in the BEMER groups (i.e. BEMER and OMT+BEMER) will receive treatment 5 times per week for a period of 3 weeks. Finally, subjects in the Placebo group will receive the combined light touch and BEMER sham treatments at same intervals as the corresponding experimental groups. OMT, BEMER, and placebo treatments will be performed by osteopathic medical students who have completed additional training given by a licensed osteopathic physician, to ensure uniform technique. All treatments will be performed during the span of three consecutive weeks.
  - c) Subjects will complete brief questionnaires regarding neck pain and quality of life before the beginning of study and will complete the same questionnaires following the completion of the three week treatment (Appendices C, E, F).

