### III. Analysis

#### A. Study Statistics

1. Primary outcome variable
  - a) Questionnaire ratings before and after treatments
    - (1) Neck Disability Index (Appendix E) [28-31]
    - (2) SF-12 Health Survey (Appendix F) [32]
    - (3) Visual Pain Analog (Appendix C) [33]
2. Statistical plan including sample size justification and interim data analysis
  - a) Paired T-tests (N~10 subjects) to investigate the changes in neck pain after each treatment protocol.
  - b) One-Way ANOVA to investigate any statistically significant differences between the means of each of the 4 experimental groups.
3. Early stopping rules

- a) Any adverse effect, as determined by the attending licensed osteopathic physician. No adverse effects are anticipated.
- B. Blinding
  - 1. All outcome analyses will be performed in a blinded fashion. Subject survey and corresponding data will be de-identified and analyzed retrospectively by investigators with no exposure to the treatment sessions. Doing so will eliminate bias associated with investigator self-interest and ensure subject anonymity.

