### **II. Costs**

A. Payment to subjects:

1. BEMER Pro Set: \$6410

2. 3 week compensation: \$50 per individual (estimating 40) = \$2,000

B. Total = \$8410

C. All paid by grants TBD

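### The between-arm one-way ANOVA has no baseline term and does not say whether it compares final scores or changes; adjusting for the baseline score would add precision at almost no cost

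*Combined protocol and SAP*

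**What the plan says.** Section II.A.3.c (Experimental Sessions) makes a baseline available for every subject: "Subjects will complete brief questionnaires regarding neck pain and quality of life before the beginning of study and will complete the same questionnaires" after the three weeks of treatment. Section III.A.1 defines the outcome only as "Questionnaire ratings before and after treatments" on three instruments (NDI, SF-12, VAS). No derived endpoint, such as post-treatment score or change, is specified.

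Section III.A.2 has two analysis lines. The first is within arm: "Paired T-tests (N~10 subjects) to investigate the changes in neck pain after each treatment protocol". The second is the only between-arm analysis: "One-Way ANOVA to investigate any statistically significant differences between the means of each of the 4 experimental groups". No covariate, ANCOVA, repeated-measures model or stratification by baseline severity appears anywhere in the protocol. Baseline is used explicitly only in the paired t-tests, and these do not compare arms.

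**The concern.** The stated purpose is to examine the individual and combined effects of OMT and BEMER, which requires comparison between arms, so this one line carries the trial's main conclusion. As written, its model has arm as the only factor.

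Two things are at stake. The first is precision: a pre-treatment score on the same scale usually explains part of the variation in the post-treatment score, and the plan leaves that unused or uses it only by subtraction. The second is the particular randomisation that occurs. Entry requires only current neck pain, with no minimum score, and arms are small, so the arms may start at visibly different levels. How such a gap affects the result depends on whether final scores or changes are analysed. The plan leaves that choice open, so it could be made after the data are seen.

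**Working it through.** **Inputs from the protocol.** About 10 subjects per arm (III.A.2.a) and a budget line "estimating 40" (Payment and Costs, II). These agree: 4 × 10 = 40, and 40 × $50 = $2,000. Section I.C.3 says "subjects will be randomized into one of the four groups: OMT, BEMER, OMT+BEMER, and Placebo", without a ratio.

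**Assumptions.** Equal allocation with all 40 analysed; two-sided 5%; 80% power for a single pairwise contrast without multiplicity adjustment; equal SDs before and after; before-after correlation r = 0.5, range 0.3 to 0.7. The protocol gives no alpha, power, effect size, SD or correlation. Its figure of about 10 therefore cannot be reproduced, and everything below is in SD units.

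**Step 1: residual variance** (outcome variance = 1).
- Final-score ANOVA: 1.
- Change-score ANOVA: 2(1 − r).
- ANCOVA: (1 − r²) × (1 + 1/34). The last factor, 1.0294, is the average cost of estimating the baseline slope with 40 subjects in 4 arms.

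| r | Final | Change | ANCOVA |
|---|---|---|---|
| 0.3 | 1 | 1.40 | 0.91 × 1.0294 = 0.937 |
| 0.5 | 1 | 1.00 | 0.75 × 1.0294 = 0.772 |
| 0.7 | 1 | 0.60 | 0.51 × 1.0294 = 0.525 |

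**Step 2: detectable pairwise difference.** The standard error is √(variance × 2/10). The noncentral t gives a multiplier of 2.879 on 36 df (unadjusted) and 2.881 on 35 df (ANCOVA).
- Final: 2.879 × √0.2 = 2.879 × 0.447 = 1.29 SD at every r.
- Change: 2.879 × √(1.40 × 0.2) = 1.52 SD; 1.29 SD at r = 0.5; 1.00 SD at r = 0.7.
- ANCOVA: 2.881 × √(0.937 × 0.2) = 1.25 SD; 1.13 SD at r = 0.5; 0.93 SD at r = 0.7.

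**Step 3: equivalent sample size**, 40 × (unadjusted variance) / (ANCOVA variance), for r = 0.3, 0.5, 0.7.
- Against final scores: 40/0.937 = 43; 40/0.772 = 52; 40/0.525 = 76.
- Against changes: 40 × 1.40/0.937 = 60; 40 × 1.00/0.772 = 52; 40 × 0.60/0.525 = 46.

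**Step 4: omnibus F test**, one arm differing from the other three by 1 SD, for r = 0.3, 0.5, 0.7. Power is 57% throughout for final scores; 43%, 57%, 81% for changes; 60%, 69%, 86% for ANCOVA.

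**Step 5: chance baseline gaps.** The difference between two arm means at baseline has SD √(2/10) = 0.447. A given active-placebo pair is then at least 0.5 SD apart with probability 26%, and at least one of the three such pairs with probability 54% (by simulation). A 0.5 SD gap shifts the comparison by 0.5r for final scores (+0.15, +0.25, +0.35 SD at r = 0.3, 0.5, 0.7). For changes the shift is 0.5(r − 1), which is −0.35, −0.25, −0.15 SD. The signs are opposite. ANCOVA removes this shift on average.

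**Step 6: where the gain disappears.**
- Against final scores at r = 0.1: 2.881 × √(0.99 × 1.0294 × 0.2) = 1.30 SD, marginally worse than 1.29. At r = 0 ANCOVA with 10 per arm is worth 10/1.0294 = 9.7.
- Against changes with follow-up SD 1.3 times baseline and r = 0.7: the change variance is 1 + 1.69 − 2 × 0.7 × 1.3 = 0.87 and the ANCOVA variance is 1.69 × 0.51 = 0.862. The ratio is 0.99 before the slope cost, so nothing is gained.
- With follow-up SD 0.7 times baseline and r = 0.7: 0.51 against 0.49 × 0.51 = 0.25, a larger gain than under equal SDs.

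**The case against.** The strongest reply is that nothing here is an error. A reader might infer from the missing covariate that the ANOVA is biased or that its type I error is wrong. The protocol does not support that: subjects are randomised, and an unadjusted comparison of randomised arms is unbiased over randomisations with its nominal error rate. This part of the reply stands.

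A reader might also infer that baseline data are ignored altogether. That is not established either. The outcome is described as ratings before and after, and the line above the ANOVA speaks of changes, so an ANOVA of change scores is a natural reading, with baseline entering by subtraction. This narrows the point but does not remove it. At equal SDs, 2(1 − r) exceeds 1 − r² for every r below 1, and a baseline gap still carries through with the sign reversed. The plan should also say which quantity it analyses.

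Third, the 26% and 54% might be taken to mean that imbalance dominates the trial or that the result is likely to be wrong. They are chances of a baseline gap only. At r = 0.5 a 0.5 SD gap moves the comparison by 0.25 SD, against an unadjusted standard error of 0.447 SD that already allows for chance imbalance.

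Finally, the size of the gain rests on a correlation that the protocol does not give, and one value of r is applied to three different instruments, including an SF-12 with four-week recall given about three weeks apart. That stands too, and is why a range is shown. Against final scores at r = 0.3 the improvement is only 1.29 to 1.25 SD, about 3%.

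**Conclusion.** The point holds as a matter of efficiency and pre-specification. The sole between-arm analysis has no baseline term and an undefined endpoint, in a trial that already collects the baseline scores. At r = 0.5 with equal SDs, adjustment lowers the detectable difference by about 12% (1.29 to 1.13 SD) on either reading, equivalent to about 12 additional subjects. Over r = 0.3 to 0.7 the equivalent sample size runs from 43 to 76 against final scores and from 60 to 46 against changes. The gain is negligible against final scores when r is near 0, and against changes when r is high and the follow-up SD exceeds the baseline SD.

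The absence of a covariate is certain; the size of the benefit is conditional on these assumptions and on 10 analysed subjects per arm. Adjustment does not make the trial well powered: 1.13 SD is still a large difference to need. This is a near-free improvement that should be made, not a condition for the analysis to be valid.

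**What to change.** Replace III.A.2.b with a sentence to this effect: for each instrument score (for the SF-12, each score that will be reported), arms are compared by an ANCOVA of the post-treatment score on arm and the baseline value of the same score, plus any factor used to stratify randomisation; adjusted arm differences are reported with 95% confidence intervals, and every between-arm statement comes from this model. This also settles the endpoint. With baseline as a covariate, analysing change gives the same adjusted arm differences as analysing the post-treatment score, so a sponsor who prefers to report change loses nothing.

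Cost: one sentence, no new data, and 1 of the 36 residual degrees of freedom. It should be written in before outcome data are examined, because a covariate chosen afterwards is less credible.

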H. OMT, BEMER, and placebo will be performed by osteopathic medical students who have completed additional training given by a licensed osteopathic physician to ensure uniform technique. A licensed osteopathic physician will be in the vicinity of the treatment location at all times while treatments are being given.

I. All data collection logs will be de-identified of personal information and only contain the randomized participant ID number linking the participant to the data collected.

J. The identifying information will be maintained by the principal investigator in a locked cabinet, which they alone have access to.

II. Study Procedures and Timeline

A. Study duration

1. The study duration is three weeks. The subjects will be required to have either OMT, BEMER, OMT+BEMER, or Placebo treatments during the course of the study. Each subject in the OMT groups (i.e. OMT and OMT+BEMER) will receive treatment 3 times per week for a period of 3 weeks. Subjects in the BEMER groups (i.e. BEMER and OMT+BEMER) will receive treatment 5 times per week for a period of 3 weeks. Finally, subjects in the Placebo group will receive the combined light touch and BEMER sham treatments at same intervals as the corresponding experimental groups. OMT, BEMER, and placebo treatments will be performed by osteopathic medical students who have completed additional training given by a licensed osteopathic physician, to ensure uniform technique.
2. Recruitment:
  - a) LECOM-Bradenton faculty, staff, osteopathic medical, dental, pharmacy, and master's students will be informed via email of the opportunity to participate in the research study and will be given contact information to confirm eligibility with a study coordinator (Appendix A).
3. Experimental Sessions
  - a) Following written consent (Appendix B), subjects will be given a randomized study ID number. They will be randomized into their treatment group.

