## **Consent Process and Privacy Protection**

- I. Consent Process
- A. Participants will be introduced to the study through classroom announcements and recruitment emails. If they decide to participate we will provide participants with a written informed consent form (Appendix B) for them to read. In addition, a researcher will thoroughly explain the study to them to ensure that the subject is willing to participate in the experiment. The participant will then sign the form after comprehension is assessed via verbal reiteration and opportunity has been provided for questions.
- II. Privacy Protection/Confidentiality
- A. Any document that can be identified with the participant including informed consent, written contact information, and project data will be stored in a locked filing cabinet in the principal investigator's office. It will remain confidential unless provided with the participant's permission or required by law. Three years after completion of the study, any personal identifiers (names, addresses, birth dates, phone numbers, etc.) will be destroyed. A secured Google Drive account will be utilized to collect de-identified data throughout the study. Access to this account is exclusive to the Principal Investigator, Principal Co-

Investigator and designated medical students as identified in the IRB. All electronic submissions of de-identified data will be treated in the same manner as stated above regarding written information.

B. All participants will be given a numerical subject ID to ensure anonymity. Both recorded and survey data will be labeled with study number only. This ID will also be kept in a secured, locked filing cabinet, and only the Principal Investigator will have access to these documents. The materials will be saved for three years and then shredded.

C. Members of the research team have completed the required CITI training modules prior to working on the proposed research. Identity unlinking procedures and use of de-identified database ensure that the results of surveys and patient demographics remain confidential.

D. We will not be making any photograph, audio, or video recordings of participants without participant consent.

E. Our study does not involve collection of data that might produce a regulatory mandate or duty to inform authorities about potentially harmful or illegal activities.

F. Certification of Confidentiality and application for Federal Exemption to Reporting are unnecessary.

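### The blinding of the outcome analysis is not secured by the means the plan gives for it: de-identification and absence from the sessions hide the person, not the arm

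*Combined protocol and SAP*

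**What the plan says.** Analysis III.B.1 (Blinding) opens with a general commitment: "All outcome analyses will be performed in a blinded fashion". The means follow in the next sentence: "Subject survey and corresponding data will be de-identified and analyzed retrospectively by investigators with no exposure to the treatment sessions". The benefit claimed is absolute: "Doing so will eliminate bias associated with investigator self-interest and ensure subject anonymity".

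The analyses to which this applies are in III.A.2. Within arms: "Paired T-tests (N~10 subjects) to investigate the changes in neck pain after each treatment protocol". Between arms: "One-Way ANOVA to investigate any statistically significant differences between the means of each of the 4 experimental groups".

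Methodology I.I describes de-identification: "All data collection logs will be de-identified of personal information and only contain the randomized participant ID number". Consent Process and Privacy Protection II.A places the de-identified data on a shared drive used throughout the study. Access is limited to the principal investigator and a group that ends with "Investigator and designated medical students as identified in the IRB". Methodology I.C.2 says who delivers the interventions: "All treatments will be performed by osteopathic medical students". The last paragraph of the Review of Literature calls the study single-blinded without saying which party is blinded.

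**The concern.** Analyst blinding means that whoever makes the analytic decisions does not know which group is which. Taking out names protects confidentiality, and staying away from the sessions removes first-hand knowledge of who was treated how. Neither masks a group column in a data file.

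This matters more when the analysis is loosely specified, as here. A decision maker who can see which group is OMT and which is placebo can be swayed, knowingly or not, on points the plan leaves open. That is the bias III.B.1 says is eliminated. A report that called the analysis blinded would rest on a procedure the protocol does not describe. The point concerns the analyst only; whether subjects can recognise the sham is a separate matter.

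**Working it through.** The plan gives no figure to reproduce here. The check sets the provisions side by side, with a little arithmetic.

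**1. What de-identification hides.**
- Methodology I.C.1: the coordinator assigns a study number so that the participant is not identified.
- Methodology I.I: logs carry that number and no personal information.
- Methodology I.J and Privacy Protection II.B: what is locked away with the principal investigator is identifying information and the subject ID.

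In each case the protected item is the person. The arm is not mentioned.

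**2. What the analyses need.** With about 10 subjects in each of 4 arms, N is about 4 × 10 = 40, which agrees with the 40 budgeted under Costs.
- Paired t-test in arm g: t = mean change in g / (SD of change in g / √n_g), with about 10 − 1 = 9 degrees of freedom.
- One-way ANOVA: F = [Σ n_g (mean_g − grand mean)² / (4 − 1)] / [Σ Σ (y_ig − mean_g)² / (40 − 4)], with 3 and 36 degrees of freedom.

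Both need to know which subjects belong together, so a group variable must be joined to the scores. Neither needs the true name of the group: F sums over g and is unchanged if the four labels are permuted.

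**3. Is the name masked anywhere?** I looked for coded arm labels, a holder of the allocation list separate from the analysts, a point at which a code is opened, and analysis choices fixed before that point. None is described.

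**4. Who can see the data.** Treatment is given by medical students (Methodology I.C.2; I.D.3 speaks of 4 to 6 of them). Designated medical students have drive access (Privacy Protection II.A). The documents do not say whether these groups overlap, nor whether the drive holds allocation.

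**5. What knowledge of the labels could influence.**
- Removal: section III.A of the subject-removal criteria removes subjects who do not follow the full regimen. It does not say how a missed or rescheduled session counts, or who decides. This choice is made subject by subject.
- Score: III.A.2.b does not say whether the means compared are post-treatment values or changes.
- Emphasis: three instruments stand under one primary outcome. If each is tested, there are 4 × 3 = 12 paired tests and 3 ANOVAs. No follow-up procedure is named for the 4 × 3 / 2 = 6 possible pairs of arms.

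**6. Would codes alone suffice?** Sections II.A.1 and II.A.3 of Study Procedures and Timeline give OMT 3 × 3 = 9 sessions and BEMER 5 × 3 = 15; the combined arm has 9 OMT and 15 BEMER. A session log would therefore separate at least OMT alone from BEMER alone, even under codes. The documents do not say whether logs reach the analyst.

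**The case against.** The plan does commit to blinded analysis, and by-arm tests can be run on groups labelled A to D. It never says that analysts will see true arm names. This stands: a reader might infer that the analysis will be unblinded, and the documents do not show that. They show only that the means named do not achieve blinding and that no other means is given.

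A reader might also infer that treating students will have access to the scores. That is not supported. III.B.1 keeps people exposed to the sessions out of the analysis, drive access is restricted to persons listed with the IRB, and belonging to the same student body is not evidence of overlap. The documents are silent on the question.

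A third tempting step is to attach an inflated false-positive rate, by supposing that the analyst takes the smaller p-value from post and change scores, or the smallest across three instruments. That inflation comes from unspecified scoring and several primary instruments. Because F does not change under relabelling, it would be the same for an analyst who saw only codes. It does not measure the cost of knowing the arms.

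Finally, the outcomes are questionnaires that subjects complete themselves, and Appendix E fixes the Neck Disability Index scoring, so the analyst rates nothing. Using analysts who did not treat does remove one source of bias. Both points stand, and they limit the weight of the concern without supporting a claim that bias is eliminated.

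**Conclusion.** The concern holds in this form: III.B.1 claims blinded outcome analysis and elimination of self-interest bias, but the two means it names leave the arm unmasked in analyses that require it, and nothing else in the protocol masks it. The blinding is not secured as described.

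The size cannot be given as a number, since it depends on how far knowledge of the labels would guide removals, choice of score and emphasis. I judge it moderate: outcome ascertainment is not affected, but those choices are open. The conclusion assumes that no separate masking procedure exists outside the protocol; if one does, the remedy is to write it in. It does not rest on any overlap between treating students and those with data access. The change should be made, because it is nearly free and makes the claim true.

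**What to change.** Rewrite III.B.1 to say that:
- a person who is not an analyst holds the allocation list and replaces the arm names by codes A to D;
- analysts receive only the codes, without session logs;
- score, analysis set and model are fixed before any by-group result is seen, and the outcome tables are produced before the code is opened;
- students who treat have no access to questionnaire scores until the code is opened.

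Replace *will eliminate* with *is intended to reduce*.

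The third item is needed as well as the coding: codes guard against choices driven by the labels, but only prior specification guards against choices driven by the p-value. The cost is one recoded column, a folder permission and protocol wording. No study procedure for participants changes.
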